3 STATISTICAL METHODS

3.1 Statistical analysis strategy

The statistical analyses will be performed in accordance with the ICH E9 guideline and will be based on the pooled data from the individual study sites, unless otherwise stated.

Medpace will perform the statistical analysis of the efficacy, safety, and antibodies data.

Overall, the analysis strategy is to evaluate safety and efficacy of Dysport compared to Placebo after single administration (DB period), and to evaluate efficacy and safety over repeated Dysport treatments, using analyses by Active Treatment Cycle.

Listings will be presented by subject for DB and OL periods together while the tables associated with the DB period will be separated from the tables assessing repeat treatment with Dysport.

Only descriptive statistics of Stage 1 data will be provided.

Double-Blind Period (Stage 1 Cycle 1) Analyses

For the analysis of the DB period, tables will be displayed using the following treatment group (DB treatment group) labels, in the following order:

- Placebo: placebo groups from all cohorts will be pooled, including for mVPAQ pain, mVPAQ life interference and mFSFI pain domain of cohort 1 despite the change in recall period and time of assessments (see protocol version 3.0).
- Dysport
 - Groups by dose (Dysport 100U, 300U, 400U, 500U, etc.)
 - All Dysport

[figure not shown]
Note: Cohort 1 (100U), 2 (300U), 3 (400U) and 5 (500U) included PVD2 subjects only. Cohort 4 (400U) and 6 (500U) included PVD1 subjects only.

Repeat treatment: Active Treatment Analyses

To assess efficacy and safety data over repeat treatments, data will be analysed using the Active Treatment Cycle approach as described in [Figure 1](#) below. These analyses will be performed on the Active Treatment population:

- for subjects treated with Dysport in the DB period, the first cycle in the DB period will be the first Active Treatment Cycle.
- for subjects treated with placebo in the DB period, the first cycle in the OL period will be the first Active Treatment Cycle.

[Figure 1](#) Active Treatment Cycle Analysis

Three types of summary tables will be produced:

- Summary by number of active treatment cycles: these tables will present the long-term efficacy and safety data with all doses combined, and will display subjects with at least 1 (2, 3 and 4) active treatment cycles.
- Summary by dose received at each active treatment cycle: to evaluate the safety of each dose at a given cycle.

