3.9 Safety

For the DB period, summary tables by DB treatment group will be provided on the Safety population.

For the Active Treatment Cycle, summary tables by number of active treatment cycles will be provided on the Active Treatment population. Additionally, a summary table will be also provided by dose received at each active treatment cycle on the Active Treatment population.

The summary tables will follow the strategy specified in Section 3.1.

3.9.1 *Extent of exposure*

To describe the duration of exposure, three durations of exposure will be calculated.

- Duration of study treatment exposure will be defined in weeks as:
(The date of last visit attended – treatment cycle 1 injection date + 1) / 7.
- Duration of treatment cycle will be defined in days as:
For subjects who are retreated at the end of the cycle, the duration of treatment cycle is calculated as (date of retreatment) - (treatment injection date).
For subjects who are not retreated at the end of the cycle, the duration of treatment cycle is calculated as (last attended visit date of the treatment cycle) – (treatment injection date) + 1.
- Duration of Active Treatment exposure will be defined in weeks as:
(The date of last visit attended – first Dysport injection date + 1) / 7.

The following summary tables will be provided:

- Description of study treatment exposure by DB treatment group + overall subjects on the safety population for DB period and overall subjects for the whole active treatment periods.
Study treatment exposure will be described both as a quantitative and qualitative variable.

- Description of duration of treatment cycle, for each treatment cycle, dose received of each treatment cycle and overall subjects from the safety population.
- Description of duration of treatment cycle, by dose received at the cycle and all doses combined on the active treatment population.
Active Treatment exposure will be described both as a quantitative and qualitative variable for each period of exposure.
- A summary table with the total number of subjects who received 1, 2 or 3 active treatment cycles and the total number of subjects who received at least 1, 2 or 3 active treatment cycles, all doses combined on Active treatment population and by DB treatment group + overall subjects.

To describe the doses received, the following summary tables will be provided:

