- Description of the actual dose received in each cycle by DB treatment group and overall subjects from the safety population.
The number and percentage of subjects receiving the actual dose will be provided.
- Description of the actual dose at each active treatment cycle, by treatment received for the active treatment cycle and overall subjects from the safety population.
The number and percentage of subjects receiving the actual dose will be provided for each active cycle.
- A listing of exposure data will also be provided.

3.9.2 *Adverse events*

Adverse events will be coded using the Medical Dictionary for Regulatory Activities (MedDRA) latest version (23.0 or later) and presented by MedDRA preferred term and system organ class.

AEs will be classified as treatment-emergent AEs (TEAEs) according to the rules below:

- Events with start date (and time) on or after the date (and time) of first IMP administration.
- Events whose severity worsens on or after the date (and time) of first IMP administration.

A TEAE that occurs under a particular treatment cycle and worsens in intensity under a different treatment cycle will be considered as treatment emergent under the two treatment cycles. In the event of another occurrence of a TEAE with a change in intensity under a different treatment cycle, the subject will also be counted in that different treatment cycle. A given AE will be assigned to the dose received prior to the onset of the AE in the designated treatment cycle.

An overall summary table of all adverse events will be presented (as described in Section 3.9) and include the following:

- Subjects with any TEAEs,
- Subjects with any TEAEs by maximum intensity,
- Subjects with any TEAEs related to IMP,
- Subjects with any TEAEs related to IMP by maximum intensity,
- Subjects with any TEAEs leading to drug withdrawal,
- Subjects with any SAEs,

- Subjects with any TEAEs leading to death,
- Subjects with any SAEs related to IMP,
- Subjects with any TEAEs of special interest (AESIs).

This summary table will be also be provided by dose received at each active treatment cycle.

All TEAEs will be summarized with the number and percentage of subjects with adverse events classified by primary system organ class and preferred term. The number of occurrences of a TEAE will also be presented. This summary table will also be provided by dose received at each active treatment cycle.

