Summary tables will also be presented by SOC and PT for SAEs, TEAEs by intensity, TEAEs by causality, and non-serious TEAEs with at least 2 subjects. TEAEs will also be summarized by decreasing overall PT frequency

If the intensity or causality is missing for a TEAE, it will be considered as missing in the summary tables. In the event of multiple TEAE being reported by the same subject within the same SOC/PT, the maximum intensity (severe > moderate > mild > missing) and the most serious causality (related > not related > missing) will be chosen.

Listings will be presented and sorted by DB treatment group, subject ID, start date of AE, primary system organ class, preferred term and verbatim text for all adverse events recorded during the study. Other information collected, such as end date and outcome of AE, will be provided in the listings.

Listings of SAE, adverse events leading to discontinuation from the study, clinically significant events, adverse events leading to drug withdrawal and death will also be presented.

TEAEs will be identified in the adverse events listings. Pre-treatment AEs and clinically significant AEs will also be flagged in the AE listings.

Adverse Events of Special Interest (AESIs)

Adverse events of special interest (AESIs) for Dysport in this study are defined as:

- Any TEAE that suggests a possible remote spread of effect of the toxin, or
- Any TEAE related to urinary incontinence or faecal incontinence, or
- Any TEAE assessed as a potential hypersensitivity reaction,

where there is a reasonable possibility of causal relationship with treatment with Dysport, regardless of the investigator reported causality.

The method described below is used for identification and analysis of events that may be qualified as TEAEs that suggest a possible remote spread of effect of the toxin, events related to incontinence or faecal incontinence or events suggestive of hypersensitivity like reactions.

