TEAEs due to possible remote spread of the effects of Dysport will be identified using the list of MedDRA preferred terms (PTs) compatible with the mechanism of action of BTX-A and based on the recommendations from the Committee for Medicinal Products for Human Use (CHMP) and the Food and Drug Administration (FDA). TEAEs potentially representing hypersensitivity reactions will be identified using the Standardised MedDRA Query (SMQ) (narrow search query) for hypersensitivity reactions. TEAEs that are possibly related to urinary incontinence or faecal incontinence will also be identified using the list of MedDRA preferred terms.

The list of MedDRA preferred terms used to identify any potential AESI is provided in *AESIs MeDDra.xlsx*.

All TEAEs identified using the search strategy described above will be medically evaluated during the study before the database lock and unblinding, by the sponsor to identify events which could possibly represent “remote spread of effect of toxin”, or which are suggestive of “related to urinary incontinence or faecal incontinence” or “hypersensitivity reactions” due to study treatment administration. Events will be disregarded as an AESI if they are confounded by the presence of alternative clinical aetiologies (medical history, concomitant medication or diagnosis which could account for the symptoms); if they are considered to be local effects instead of distant spread, as judged by the site of injection; the time period between the last study treatment administration and event onset is not in accordance with the expected mechanism of action; or due to insufficient information/evidence to make an assessment.

In the summary data tabulations and listings, only the final list of AESIs confirmed by the sponsor as “a possible remote spread event”, “hypersensitivity reactions” or “urinary incontinence and faecal incontinence” will be taken into account.

Besides the AESI listing, a summary table of AESI will be presented by SOC and PT (as described in Section 3.9) and include the following:

- Subjects with any AESI suggesting a possible remote spread of effect of the toxin,
- Subjects with any AESI related to urinary incontinence or faecal incontinence,
- Subjects with any AESI assessed as a potential hypersensitivity reaction.

3.9.3 ***Laboratory data***

All laboratory data will be presented in the units of International System of Units (SI).

The following summaries will be provided:

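### The SAP's ground for discarding local effects from the AESI list is not limited to remote spread, so as written it can also remove incontinence events

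*SAP*

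**What the plan says.** SAP 3.9.2 lists three AESI classes joined by *or*. The second stands alone: "Any TEAE related to urinary incontinence or faecal incontinence, or". Protocol 8.1.4 has the same three classes.

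The SAP finds candidate events by preferred-term lists for remote spread and incontinence and by a standard MedDRA query for hypersensitivity. Everything found goes to one medical review by the sponsor, before database lock and unblinding. The exclusion sentence then opens "Events will be disregarded as an AESI if they are confounded by the presence of alternative clinical aetiologies" and adds three more grounds: the event is local, its timing does not fit the mechanism of action, or there is too little information. The local ground reads "if they are considered to be local effects instead of distant spread, as judged by the site of injection".

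The outcome of the review decides what is reported: "In the summary data tabulations and listings, only the final list of AESIs confirmed by the sponsor" counts. The outputs concerned are the AESI listing, the AESI table with its planned row "Subjects with any AESI related to urinary incontinence or faecal incontinence", and the line in the overall adverse event summary for subjects with any AESI.

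**The concern.** Whether an effect is local or distant is the right question for deciding if an event shows remote spread. It is the wrong question for incontinence, which is an AESI whether or not toxin has travelled.

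The injections go into pelvic floor muscles, and Protocol 1.4 says that incontinence may be seen after injection there. It also says that local spread makes the safety profile depend on the injection site. A reviewer applying the exclusion sentence as written could therefore judge an incontinence event local and discard it.

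The AESI definition requires a reasonable possibility that Dysport caused the event. An event judged a local effect of the injection meets that requirement. The other three grounds question causality or the quality of the evidence; this one can remove an event whose link to treatment is accepted.

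At stake is the one planned table row that counts subjects with any incontinence together, in a stage whose primary objective is safety.

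**Working it through.** **Scope of the rule.** The plan states no figure to reproduce, so the check is a comparison of texts.

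| Step | SAP 3.9.2 | Limited to one class? |
|---|---|---|
| Definition | Three classes, incontinence on its own | Not applicable |
| Search | Incontinence terms have their own preferred-term list | Not applicable |
| Review | All events found by any search, one review naming all three classes | No |
| Exclusion | Four grounds applied to events in general | No, for all four |
| Output | Sponsor-confirmed AESIs only | No |

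Applied literally, an incontinence TEAE is found by the term list, reviewed, judged local by injection site, discarded, and so absent from the AESI listing, the incontinence row and the AESI line of the overall summary.

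**Comparison with the protocol.** Protocol 8.1.4 has no such ground. It names location of administration only as something to consider, and gives the purpose of the review as judging remote spread or hypersensitivity. The SAP adds incontinence to the review and turns locality into a ground for exclusion. SAP section 5 records no change to AESI handling.

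**Where the events remain.** They stay in the TEAE tables by system organ class and preferred term (also by dose at each active cycle), in the intensity and causality tables, and in the AE listings. Those meeting the definition in Protocol 3.1.1.1 are also listed and flagged as clinically significant. For incontinence in its own right that requires a duration of more than 4 days.

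**Sensitivity to one subject.** SAP 3.9 states: "For the DB period, summary tables by DB treatment group will be provided on the Safety population". The SAP analyses cohorts 1 to 6. For the dose of each cohort, SAP 3.1 notes "Cohort 1 (100U), 2 (300U), 3 (400U) and 5 (500U) included PVD2 subjects only", with PVD1 subjects in cohorts 4 (400 U) and 6 (500 U). Protocol 3.1.1 plans 8 Dysport and 2 placebo subjects per cohort, except cohort 4 with 6 and 2.

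- 100 U: 8. 300 U: 8.
- 400 U: 8 + 6 = 14. 500 U: 8 + 8 = 16.
- All Dysport: 8 + 8 + 14 + 16 = 46.
- Pooled placebo: 6 × 2 = 12.

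If a subject's only incontinence event is discarded, the row falls by 1/n. Protocol 3.1.1 lets one additional screened subject into a cohort; the last column assumes this happened in every cohort and the subject always received Dysport.

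| Group | Planned n | Fall (points) | n with extras | Fall (points) |
|---|---|---|---|---|
| 100 U or 300 U | 8 | 12.5 | 9 | 11.1 |
| 400 U | 14 | 7.1 | 16 | 6.3 |
| 500 U | 16 | 6.3 | 18 | 5.6 |
| All Dysport | 46 | 2.2 | 52 | 1.9 |
| Pooled placebo | 12 | 8.3 | 12 | 8.3 |

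Dosed subjects who were replaced would enlarge the denominators and reduce these figures further. The table covers the double-blind period only; the SAP also plans summaries by active treatment cycle, whose denominators are not given.

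**The case against.** The best reply is that the clause limits itself. A contrast between local effect and distant spread has meaning only where distant spread is the question. The surrounding text agrees: incontinence has its own class, its own search, its own place among the confirmed categories and its own table row. Protocol 8.1.4 does not use locality as an exclusion ground, and SAP section 5 declares no departure. On this view the natural reading is the one under which the section is consistent.

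As evidence of intent this is persuasive; the sponsor probably meant remote spread only. But it shows that the written rule is wider than intended. It does not supply the missing limit, and a reviewer who follows the sentence as written gets a wrong row.

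Two further points stand. No passage says that incontinence would in fact be classed as local, and the AESI term file is not part of the documents, so the loss of events is possible, not demonstrated. The 1/n figures would also hold for any subject dropped from any row; they show how sensitive small groups are, not how often this would happen.

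It is also true that no event disappears from the report. Yet tables by preferred term do not give the number of subjects with any incontinence, which is what the AESI row is for.

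**Conclusion.** The concern holds, as a minor point. The exclusion sentence in SAP 3.9.2 gives four grounds and limits none to a class, so its local-effect ground, read literally, conflicts with treating incontinence as a separate AESI class and with the row planned for it.

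The number of events affected cannot be estimated: the documents give neither an incontinence rate nor a local or remote classification of incontinence. The per-subject falls assume that the Safety population equals the planned evaluable numbers, because actual numbers are not given.

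The consequence is confined to the AESI outputs. Stage 1 is descriptive with no formal testing, the study ended before Stage 2, and the review precedes unblinding. No test or dose decision depends on the count.

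**What to change.** In SAP 3.9.2, attach the local-effect ground to events reviewed for the remote-spread class, and state that it does not apply to urinary or faecal incontinence. Leave the other three grounds as they are. Make the change before the AESI list is finalised.

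The cost is one qualifying phrase. It needs no new tables, and no entry in SAP section 5, since it brings the SAP closer to Protocol 8.1.4. The only downside is that the reported AESI count may be slightly higher.

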### 3.2.3 Safety Endpoints and Evaluations

The safety and tolerability of Dysport will be assessed throughout the study by evaluating:

- Incidence of treatment emergent AEs (TEAEs), serious AEs (SAEs), clinically significant AEs, DLEs, AEs (or SAEs) leading to discontinuations and AEs of special interest (AESIs).
- Absolute values, values classified as abnormal/normal and change from Baseline in the clinical laboratory test results (including nonfasting clinical biochemistry and haematology parameters).
- Number of subjects who seroconvert for BTX antibodies following treatment with Dysport.
- Clinical evaluation of concomitant medication usage (except rescue medication) and therapies.

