Urine test for illicit drugs	X			X						X	
PCS	X										
PGI-S [e]*	X	X		X	X	X	X	X	X		
PGI-C [e]*				X	X	X	X	X	X		
eDiary mVPAQ pain subscale [e]*	X	X		X	X	X	X	X	X		
eDiary mVPAQ life interference subscale [e]*	X	X		X	X	X	X	X	X		
eDiary mFSFI pain domain [e]	X	X		X	X	X	X	X	X		
mVPAQ subscales (except pain and life interference) [f]*	X	X		X	X		X			X	
mFSFI domains (except pain) [f]*	X	X		X	X	X	X	X	X		
eDiary relationship/partner status [g]*	X	X		X	X	X	X	X	X		
eDiary dilator insertion [k]*	X	X		X	X	X	X	X	X		
PHQ-9*		X			X					X	

Study Procedures and Assessments	Pretreatment		Double-Blind Treatment Period Cycle 1							End of Cycle 1/ EOS or EWD [b]	
	V1	V2	V3	V4	V5 [a]	Additional Visits [a]					
						V6	V7	V8			
Visit Day/Week No.	Screening (Day -14) [m]	Baseline (Day 1)	Week 2 (Day 15)	Week 6 (Day 43)	Week 12 (Day 85)	Week 18 (Day 127)	Week 24 (Day 169)	Week 30 (Day 211)	Week 36 (Day 253)		
Type of visit	Clinic	Clinic	Telephone	Clinic	Clinic	Clinic	Clinic	Clinic	Clinic		
Visit Window	-14 days/ +3 days		±3 days	±5 days	+14 days	±14 days	±14 days	±14 days	±14 days		
SF-36*		X			X					X	
eDiary intercourse details [h]*	X	X		X	X	X	X	X	X		
Q-tip test	X										
Dilator test	X	X		X	X	X	X	X	X		
Vaginal swab	X										
Measurement of pelvic floor pressure [n]		X		X	X	X	X	X	X		
CGI				X	X	X	X	X	X		
Clinical laboratory tests (nonfasting biochemistry, haematology, FSH [i])**	X				X					X [d]	
Blood sample for antibodies**	X									X [d]	
Randomisation		X									
Study drug administration			X [j]								
Assessment for retreatment					X	X	X	X			
Subject Interviews				X [l]							

BP=blood pressure, BTX=botulinum toxin, CGI=clinical global impression, EOS=end of study, EWD=early withdrawal, FSH=follicle stimulating hormone, HR=heart rate, ICF=informed consent form, mFSFI=modified female sexual function index, incl.=inclusive, mVPAQ=modified vulvar pain assessment questionnaire, NRS=numeric rating scale, PGI=patient global impression, PHQ-9=patient health questionnaire, SF-36=36-item short form survey, V=visit.

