#### 11.4.7 Safety Evaluation

All safety data will be included in the subject data listings. Analyses and summary tables will be based upon the safety population.

All AEs will be coded according to the current version of MedDRA at the time of database lock and will be classified by MedDRA preferred term and system organ class. AE listings will be presented by subject, system organ class and preferred term.

Incidence of all reported TEAEs and SAEs will be tabulated by treatment, group, dose and overall. In addition, summary tables will be presented by maximum intensity, drug relationship and TEAEs associated with premature withdrawal of study medication.

A TEAE is defined as any AE that occurs during the active phase of the study if:

- it was not present prior to receiving the first dose of IMP, or
- it was present prior to receiving the first dose of IMP but the intensity increased during the active phase of the study.

All TEAEs will be flagged in the AEs listings.

Summary statistics (mean, median, SD and range as appropriate) by treatment group, dose and by overall will be presented for clinical laboratory tests at each assessment with change from Baseline. For laboratory data, abnormal values will be flagged in the data listings and a list of clinically significant abnormal values will be presented. Shift tables will be presented of the number and percentage of subjects with low, normal or high values and normal or abnormal exams.

The number and percentage of subjects with the presence of BTX-A antibodies (neutralising) at Baseline will be presented. The number of seroconverters (subjects who have negative results at Baseline and have at least one positive result at any one post-treatment timepoint) for neutralising antibodies will be reported.

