- A summary of the actual and change from baseline in each laboratory parameter by treatment group and timepoint,
- A summary of the number and percentage of subjects experiencing Potentially Clinically Significant Abnormalities (PCSA). PCSA criteria for laboratory parameters are defined in appendix 2,

For PCSA table, the denominator should be the number of subjects with both a baseline and a post-baseline assessment at a given timepoint.

In addition, the following listings will be provided:

- A listing of all laboratory data. Out-of-reference-range values will be flagged as high (H), low (L), clinically significant [C]. Any unscheduled laboratory assessments will be flagged as such in the listings.
- Laboratory reference ranges,
- A listing will present all values of the parameter for a subject with at least a clinically significant abnormal value for hematology and biochemistry.
- A listing of PCSA. All data for a laboratory parameter will be displayed for a subject having at least one post-baseline PCSA (with flag indicating PCSA).
- A listing will present the urine drug screening and urine pregnancy test.
- A listing will be provided for subjects with abnormal result of drug abuse test.

Any clinically significant laboratory result abnormalities observed during the study will be reported as AEs.

3.9.4 *Vital signs*

Vital signs were recorded at the Screening Visit. A listing of vital sign data by treatment group, with unscheduled vital signs flagged.

Any clinically significant vital sign abnormalities observed during the study will be reported as AEs.

3.9.5 *Physical examination*

Physical examination was done at the Screening Visit. Date of exam and overall assessment will be listed and sorted by DB treatment group, and subject ID, with unscheduled physical examination flagged.

Any clinically significant physical examination finding observed during the study will be reported as AEs.

3.9.6 *Antibodies*

The following definitions will be considered:

- **Seroconverters** are subjects with ADA titer ≤ 1 for antibody at baseline and ADA titer > 1 post-treatment.
- **Seroreverters** are subjects which ADA titer > 1 at baseline and ADA titer ≤ 1 post-treatment.
- **Treatment boosted ADA** are subjects with ADA titer > 1 at baseline that were boosted to a higher-level following IMP administration (the ADA titer is greater than 100 times the baseline titer).
- **Incidence** is defined as the proportion of seroconverters or treatment-boosted subjects.

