7 APPENDICES

7.1 Appendix 1: List of PCSA criteria

PCSA for blood chemistry parameters:

Parameter	PCSA
ALT/SGPT	$\geq 3 \times \text{ULN U/L}$
AST/SGOT	$\geq 3 \times \text{ULN U/L}$
GGT	$\geq 3 \times \text{ULN U/L}$
ALP (Alkaline Phosphatase)	$\geq 1.5 \times \text{ULN U/L}$ or $\geq 3 \times \text{ULN U/L}$
Creatinine	$\geq 150 \mu\text{mol/L}$ (Adults)
Blood Urea Nitrogen	$> 10 \text{ mmol/L}$
Chloride	$\leq 90 \text{ mmol/L}$ $\geq 115 \text{ mmol/L}$
Calcium	$< 1.75 \text{ mmol/L}$ $> 3 \text{ mmol/L}$
Sodium	$< 130 \text{ mmol/L}$ $> 150 \text{ mmol/L}$
Potassium	$< 2.5 \text{ mmol/L}$ $> 6 \text{ mmol/L}$
Total cholesterol	$> 6.22 \text{ mmol/L}$
Triglycerides	$> 2.26 \text{ mmol/L}$
HbA1c	$> 8\%$
Albumin	$\leq 25 \text{ g/L}$
Direct bilirubin	$> 2 \text{ ULN } \mu\text{mol/L}$
Total bilirubin	$> 2 \text{ ULN } \mu\text{mol/L}$
Phosphate	$< 0.75 \text{ mmol/L}$ $> 1.8 \text{ mmol/L}$
Total protein	$< 40 \text{ g/L}$

PCSA for haematology parameters:

Parameter	PCSA
White blood cell	$\leq 2.8 \text{ } 10^9/\text{L}$ $\geq 16 \text{ } 10^9/\text{L}$
Red blood cell	$< 3 \text{ } 10^{12}/\text{L}$ $> 6 \text{ } 10^{12}/\text{L}$
Hematocrit	≤ 0.32 and 0.03 decrease from baseline L/L (female) ≤ 0.37 and 0.03 decrease from baseline L/L (male)
Lymphocytes	$< 0.3 \text{ } 10^9/\text{L}$ $> 11.0 \text{ } 10^9/\text{L}$
Neutrophils	$< 1 \text{ } 10^9/\text{L}$ $> 13 \text{ } 10^9/\text{L}$
Monocytes	$> 2.3 \text{ } 10^9/\text{L}$
Basophils	$> 10^9/\text{L}$
Eosinophils	$> 10^9/\text{L}$
Hemoglobin	$\leq 95 \text{ g/l}$ (female) $\leq 115 \text{ g/l}$ (male)
Platelet count	$< 75.1 \text{ } 10^9/\text{L}$ $\geq 700 \text{ } 10^9/\text{L}$

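### The SAP's table of potentially clinically significant laboratory abnormalities does not separate new from pre-existing abnormality, and the protocol's laboratory shift tables are dropped without record

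*SAP*

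**What the plan says.** SAP 3.9.3 (Laboratory data) plans two laboratory tables. One gives actual values and change from baseline by parameter, treatment group and timepoint. The other is described as "A summary of the number and percentage of subjects experiencing Potentially Clinically Significant Abnormalities (PCSA"). For that second table the SAP adds: "For PCSA table, the denominator should be the number of subjects with both a baseline and a post-baseline assessment at a given timepoint". The numerator is not defined further.

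The accompanying PCSA listing is triggered by any post-baseline exceedance: "All data for a laboratory parameter will be displayed for a subject having at least one post-baseline PCSA (with flag indicating PCSA"). A full laboratory listing with high, low and clinically significant flags is also planned.

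The criteria are in SAP 7.1 (Appendix 1). Only haematocrit carries a condition relative to baseline. The others are fixed values or multiples of the upper limit of normal, including total cholesterol above 6.22 mmol/L and triglycerides above 2.26 mmol/L. Protocol Table 2 labels the biochemistry samples as non-fasting.

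Protocol 3.2.3 lists among the safety endpoints: "Absolute values, values classified as abnormal/normal and change from Baseline in the clinical laboratory test results". Protocol 11.4.7 plans the matching display: "Shift tables will be presented of the number and percentage of subjects with low, normal or high values and normal or abnormal exams".

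**The concern.** A table of on-treatment laboratory abnormality is read as showing what appeared after dosing. Here the baseline value serves only to admit a subject to the denominator. If the table is programmed on the literal text, a woman above a cut-off before injection and unchanged afterwards is shown in the same way as one who crossed it on treatment.

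The shift table is the usual display for separating the two, and the protocol planned one. Without it, neither remaining laboratory table makes the separation. Means and changes from baseline do not show how many subjects crossed a limit. The PCSA table shows how many were over a limit, but not how many were already over it.

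The dose groups are small, so one such subject moves a percentage visibly. A chance imbalance at baseline could look like a dose pattern, or a pre-existing abnormality in the placebo group could hide one.

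**Working it through.** The plan gives no figure to reproduce on this point, so the check compares the texts and then sizes the effect of one subject.

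**1. Does any rule use baseline PCSA status?**
- SAP 3.9.3: a baseline value is needed for the denominator, with no condition on what that value is.
- SAP Appendix 1: a change condition for haematocrit only.
- SAP 3.9.3 listing: triggered by a post-baseline PCSA, whatever the baseline status.
- By contrast, SAP 3.9.6 (Antibodies) defines seroconversion by baseline titre, restricts some percentages to subjects positive at baseline, and plans a baseline-to-end shift table.

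So the SAP applies baseline status to antibodies but not to laboratory data.

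**2. Were the shift tables removed on the record?** Protocol 11.4.7 plans them. The only shift table in the SAP is the antibody one. SAP section 5 (Changes from protocol) records removal of the centre-effect description, the intermediate and primary analyses, and the per-protocol population, and records the changed COVID-19 date. It does not mention laboratory shift tables.

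**3. When are laboratory samples taken?** Protocol 5.2.1.1 (Screening), 5.2.2.4 (Week 12) and 5.2.4 (End of Study or Early Withdrawal) include them. Protocol 5.2.2.3 (Week 6) does not. Under Protocol 5.2, Screening values serve as baseline when not repeated. The Stage 1 primary window in Protocol 3.2.1 ends at Week 6, so no scheduled post-baseline sample falls inside it.

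**4. What does one subject weigh?** Planned sizes come from Protocol 3.1.1, cohorts 1 to 6 from SAP 1.3.5, and the pooling of placebo from SAP 3.1.

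| Group | Cohorts | Planned n | One subject |
|---|---|---|---|
| Placebo, pooled | 1 to 6 | 6 × 2 = 12 | 1/12 = 8.3 points |
| 100 U | 1 | 8 | 1/8 = 12.5 points |
| 300 U | 2 | 8 | 1/8 = 12.5 points |
| 400 U | 3, 4 | 8 + 6 = 14 | 1/14 = 7.1 points |
| 500 U | 5, 6 | 8 + 8 = 16 | 1/16 = 6.3 points |

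Total: 12 + 8 + 8 + 14 + 16 = 58.

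**5. How many such subjects might there be?** The documents give no laboratory rates. Take as assumptions, for one parameter, a baseline prevalence above the cut-off of b = 5% to 15% and a persistence to the later sample of s = 50% to 100%.
- Expected count = 58 × b × s. Low: 58 × 0.05 × 0.5 = 1.45. High: 58 × 0.15 × 1.0 = 8.7. That is about 1.5 to 9 of 58.
- Chance that a group of 8 contains at least one subject over the cut-off at baseline = 1 − (1 − b)^8. At 5%: 1 − 0.95^8 = 34%. At 10%: 1 − 0.90^8 = 57%. At 15%: 1 − 0.85^8 = 73%.
- With no new abnormality at all, a table that counts baseline cases shows b × s, from 0.05 × 0.5 = 2.5% to 0.15 × 1.0 = 15%. A table restricted to subjects free of that PCSA at baseline shows 0%.

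**The case against.** The strongest reply is that the SAP does not say baseline cases are counted. A reader might infer that it does, but the numerator is simply left undefined, and requiring paired values is equally consistent with a display by baseline status. That stands. The fault is that nothing excludes or separates these subjects, so the choice falls to the programmer.

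A reader might also infer that the PCSA table was meant to take the place of the shift tables. The SAP never says so. Protocol section 11 allows the SAP to modify planned analyses, and asks for an amendment or a dedicated report section only for major changes to the primary endpoint or its analysis. What remains is an omission that SAP section 5 should have recorded.

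Four further points limit the consequence, and all stand:
- Safety is the Stage 1 primary objective, but apart from unscheduled or early-withdrawal samples, laboratory data do not enter the primary window to Week 6.
- A PCSA is a flag. Under Protocol 8.1.2.4 a laboratory abnormality becomes an adverse event only if it is clinically significant or leads to a dosing change or further work-up. The treatment-emergent rule in SAP 3.9.2 needs onset or worsening after first dosing.
- The change-from-baseline summary and the listings let a reader identify pre-existing values by hand, and placebo subjects are exposed to the same misclassification.
- Many cut-offs are extreme, such as transaminases at three times the upper limit, and exclusion criterion 18 lets investigators exclude worrying laboratory findings. Lipids are the most plausible problem rows, since no eligibility criterion sets a lipid limit.

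These points reduce the importance of the gap. They do not supply the missing table.

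**Conclusion.** The point holds as a gap in a supportive, descriptive safety display. As written, no planned laboratory table distinguishes new from pre-existing abnormality, and the protocol table that would do so is missing without explanation.

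The certain part of the size is the weight of one subject: 6.3 to 12.5 percentage points in the Dysport dose groups and 8.3 in pooled placebo. This uses planned numbers; actual denominators depend on who was enrolled and sampled. The expected count of about 1.5 to 9 of 58 rests entirely on assumed prevalence and persistence. Its upper end needs full persistence, which sits poorly with values that vary with meals.

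The documents do not support concluding that the Stage 1 primary safety assessment is compromised, or that stable baseline values would be reported as adverse events.

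**What to change.** - **PCSA table (SAP 3.9.3).** Define the numerator. Present post-baseline PCSAs by baseline PCSA status, or among subjects without that PCSA at baseline with baseline PCSAs in a separate row. The antibody definitions in SAP 3.9.6 already follow this logic.
- **Shift tables.** Restore the low/normal/high tables of Protocol 11.4.7. That section sets no timepoints, so specify baseline to the scheduled post-baseline laboratory visits: Week 12 and End of Study or Early Withdrawal. If they are not restored, record and justify their removal in SAP section 5.
- **Lipid rows.** Footnote total cholesterol and triglycerides as non-fasting. This helps interpretation but does not remove meal-related new exceedances: a woman below the triglyceride cut-off at Screening and above it after a meal at Week 12 still counts as new.
- **Cross-reference.** SAP 3.9.3 points to appendix 2 for the PCSA criteria, but the list is in Appendix 1.

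The cost is one revised derivation and one more standard table, from data already collected, with slightly smaller denominators for some parameters if the at-risk version is used.
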